1. PREFACE

The purpose of this document is to provide a Manual of Operating Procedures (MOP) for Project 3 of SMART (Pilot Test of Contingency Management [CM] and Brief Motivational Interviewing + Substance Free Activity Session Interventions + Mindfulness-Based Adherence Promotion [BSM]). The role of the MOP is to facilitate consistency in protocol implementation and data collection across participants and study staff. Use of the MOP increases the likelihood that the results of the study will be scientifically credible and provides reassurance that participant safety and scientific integrity are closely monitored.

2. AWARD AND IRB INFORMATION

2.1. Study Title

Full Title: Pilot Test of Contingency Management vs. Brief Motivational Interviewing + Substance Free Activity Session + Mindfulness-Based Adherence Promotion

Working Title: SMART Project 3.

2.2. Award Information

Funding Agency: National Center for Complementary & Integrative Health (NCCIH)

Award number: R61AT010604-01

Grant Title: Testing the Effects of Contingency Management and Behavioral Economics on Buprenorphine-Naloxone Treatment Adherence Using a Sequential Multiple Assignment Randomized Trial (SMART) Design

Grant Years:

R61: 2019-2021

R33: 2021-2024

Grant Amount: \$3,358,258

Program Director: Clinical Research – [name]

Division of Extramural Research

National Center for Complementary & Integrative Health (NCCIH)

[name]

[contact] Email: [contact]

2.3. IRB

Project number: 20-07418-XP

The University of Tennessee Health Science Center IRB (FWA00002301) approved this study on 6/30/20. The IRB Reference number is 20-07418-XP UM. IRB approval is provided in Appendix A.

2.4. Clinical Trials Registration

This study is now registered with clinicaltrials.gov, registration number, it's NCT04464421.

3. OVERVIEW

3.1. Forward

The SMART Project 3 manual includes concepts, strategies and materials that have been used in previous substance use intervention, abstinence, and medication adherence trials, including the interventions that were previously designed by our Co-PI's and their current and former colleagues. Their contribution is acknowledged with thanks to the investigators and staff involved.

It is essential that staff adhere to the Manual of Procedures (MOP) as closely as possible. This MOP is the official reference for how the SMART Project 3 study should be conducted.

Familiarize yourself with these materials. The Principal Investigator, or Project Manager can answer questions you have about the study and its implementation.

It should be noted that Interventionists have some flexibility in implementing the treatment protocol to tailor the intervention to participant needs. However, Interventionists should not modify the protocol in significant ways and should always notify the Project Manager of protocol modifications, deviations, or violations.

3.2. Objectives

Our goal with this research is to examine the feasibility, satisfaction rates, and efficacy of two interventions, Contingency Management (CM) and Brief Motivational Intervention + Substance Free Activities + Mindfulness-Based Adherence Promotion (BSM), to improve buprenorphine-naloxone adherence during the treatment initiation phase (first 5 physician visits). Once feasibility, satisfaction, and efficacy are acquired, Project 4 (the randomized clinical trial associated with the R33 award phase) will be conducted.

Feasibility in this trial is defined as the ability to recruit, treat, and follow up participants within the target timeline and costs. Recruitment, intervention, and retention actuals (vs. goals) will be evaluated by investigators and the Data Safety Monitoring Board (DSMB) which will be convened every 6 months.

Satisfaction will be measured with a measure developed from previous research.

Efficacy will be evaluated in terms of participant adherence to buprenorphine-naloxone treatment: Showing up to scheduled appointments with their physician at the Center for Addiction Science AND the presence of buprenorphine in the participant's urine screen, conducted as a part of buprenorphine treatment.

3.3. Design and Outcomes

This project will use a randomized design to compare treatment satisfaction and effectiveness of Contingency Management (CM) and Brief Motivational Intervention + Substance Free Activities Session + Mindfulness-Based Adherence Promotion (BSM) for medication adherence in patients who are initiating buprenorphine-naloxone treatment at our Center for Addiction Science (N=40). The interventions will take place across the first 4 physician visits of buprenorphine-naloxone treatment, starting after treatment intake.

Primary outcomes will include feasibility and satisfaction at the fourth weekly intervention visit, and an efficacy comparison of intervention group differences in buprenorphine-naloxone treatment adherence, defined as (1) attendance at physician visit AND (2) buprenorphine-naloxone presence in urine toxicology.

3.4. Duration

3.4.1. CM Group Course and Session Duration

Participants assigned to the CM arm will have contact with study staff at their first physician visit (intake visit at the Center for Addiction Science) and then at the following 4 physician visits that are scheduled as a regular buprenorphine-naloxone treatment course. These visits are often scheduled at 1 week, 2 weeks, 4 weeks, and 8 weeks following intake (see Figure 1). However, this varies with some patients, thus participation could potentially last 4 months as a result of them being seen on a monthly basis. Participation at each intervention session is expected to last for 10minutes for the assessment and 2 minutes for the intervention (“number wheel” gift card picker).

3.4.2. BSM Group Course and Session Duration

Participants assigned to the BSM arm will have contact with study staff at their first physician visit (intake at the Center for Addiction Science) and then at the following 4 physician visits that are scheduled as a regular treatment course. These visits are often scheduled at 1 week, 2 weeks, 4 weeks, and 8 weeks following intake (see Figure 1). However, this varies with some patients, thus participation could potentially last 4 months as a result of them being seen on a monthly basis. Participation is expected to last 10 minutes for the assessment and 30 minutes for the psychosocial intervention.

3.4.3. Final Assessment (Participant)

All participants will complete a blinded treatment satisfaction follow-up assessment shortly after completing Session 4 Part 1. Session 4 Part 2 assessment is to be conducted by an assessor blind to study conditions.

3.4.4. Final Chart Review

To examine treatment efficacy, we will also collect treatment attendance and urine toxicology information 30 days after S4 is completed (or the S4 window closes for those who do not complete the S4 intervention).

3.4.1. Figure 1.

Figure 1. Study Duration and Participant Medical vs. Study visits

3.5. Sample Size and Population

Approximately 40 participants will be recruited from UTHSC's Center for Addiction Science (CAS) for this study. We will randomize 20 participants to the CM group, and 20 participants to the BSM group.

3.5.1. Randomization

Participants are individually assigned to a study arm by block randomization (1:1 allocation, block length of 4).

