3.5.2. Inclusion/Exclusion

Participants must be 18 years of age or older and presenting for buprenorphine-naloxone treatment. Patients must be eligible to receive buprenorphine-naloxone medication (e.g., Suboxone, Bunavail, Zubsolv) during their visit at CAS. This study is open to all eligible participants.

Notably, due to the nature of medical treatment, approximately 5% of new patients will not follow the "regular" intake course of buprenorphine due to previous treatment and/or treatment initiation using injectable depot buprenorphine administration (which requires fewer physician visits). Because all patients initiating treatment are at risk for drop out/low adherence, we wish to enroll these participants if at all possible under the stringent timelines for this study. We will therefore enroll unusual buprenorphine-

naloxone initiation timelines on a case by case basis, dependent upon the ability to complete study procedures within the study timeline.

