4.3.4. Interventionists

The Interventionists ([name] and [name]) will be responsible for participant and clinic relations including recruiting, consenting, and assessing participants. [name] and [name] will conduct BSM and CM intervention and will receive weekly supervision by Drs. [name] and [name].

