8.2.3. Randomization

Once consent has been signed by the participant and study staff and the baseline assessment is complete, the staff member will randomize the participant. The randomization scheme is posted on the “SMART: Project 3 Regulatory” OneDrive file. Only appropriate staff have editing privileges for this document to avoid tampering. Participants will be immediately informed regarding the treatment arm they have been assigned to.

Participants will also be randomized to a counselor who will work with them throughout their participation in the study.

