8.6. Intervention Sessions

Prior to the session, Interventionists will prepare for the brief assessment conducted during each treatment session by finding the participant in the Filemaker database, or if offline, entering the participant information on the top of the assessment materials.

Interventionists will also prepare to administer the appropriate session (1, 2, 3, or 4) (within the appropriate condition).

In addition, Interventionists will prepare the recording device to ensure that the session is recorded. If remote, the interventionist will text or email the participant a Zoom telephone number with a meeting ID for them to call and be placed in a meeting. The interventionist will ensure that Zoom is recording once permission is granted from participant. All sessions will be recorded and uploaded to OneDrive folder (SMART Project 3/Recordings) and labeled with the participant's study ID, session number (1, 2, 3, 4), condition (CM vs. BSM), and staff initials. (e.g. 301 S2 BSM AB)

At each session , the Interventionist will meet with the participant to complete the assessment questionnaires and complete the intervention – either a BSM session or a wheel spin for additional gift cards for CM (if requirements are met).

If the participant drops out of treatment at the Center for Addiction Science, they will no longer receive the CM or BSM. However, all assessments will be conducted regardless of the participant's adherence to medical treatment at the CAS. Upon completion of the assessment, participants will still earn the \$50 gift card. This will allow us to understand the reason for the participant's non-adherence to treatment, and to evaluate whether these individuals pursue treatment elsewhere.

The intervention scripts are available in section 13 of the manual of procedures.

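### The manual that recruiting staff work from prints a single block length of 4 and restricts only editing of the posted allocation list, so upcoming assignments can be predicted and may be visible.

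*Protocol*

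**What the plan says.** Protocol section 3.5.1 gives the whole allocation method in one sentence: "Participants are individually assigned to a study arm by block randomization (1:1 allocation, block length of 4". No second block length and no stratification is mentioned. Section 3.5 gives the target: "We will randomize 20 participants to the CM group, and 20 participants to the BSM group". Section 3.1 tells staff how to regard the manual: "This MOP is the official reference for how the SMART Project 3 study should be conducted".

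On who knows what:

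- Section 4.3.4 says the interventionists "will be responsible for participant and clinic relations including recruiting, consenting, and assessing participants", and that they "will conduct BSM and CM intervention and will receive weekly supervision".
- Section 8.2.3 has the staff member randomize after consent and baseline. It then says: "Participants will be immediately informed regarding the treatment arm they have been assigned to".
- Section 8.2.3 also places the randomization scheme on a study OneDrive file. It restricts editing, to prevent tampering, and is silent on viewing.
- Section 8.6 (Intervention Sessions) has recordings from both arms uploaded to OneDrive, "labeled with the participant's study ID, session number (1, 2, 3, 4), condition (CM vs. BSM), and staff initials".
- Section 3.4.3 blinds only the assessor of Session 4 Part 2. Section 4.3.5 gives the blinded assessments to the Research Assistant, who also takes part in recruiting and consenting.

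**The concern.** With blocks always of 4, anyone who keeps count knows the last assignment of each block, and the last two whenever the first two match. Randomizing after consent and baseline gives no protection, because a forced assignment can be worked out before the next patient is approached. If the posted list can be opened by recruiting staff, no counting is needed.

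Foreknowledge matters only where staff can influence entry, and the protocol leaves some room for that. Under sections 6, 8.1 and 10, staff review the clinic schedule and may raise patients with the physician. Under section 8.2.2, baseline may be finished later by telephone. Because randomization waits for baseline, the time at which baseline is closed decides who takes the next place on the list.

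At stake is the adherence comparison, which section 3.3 lists among the primary outcomes. The SAP hypothesizes better adherence with CM and relies on preliminary effect sizes. Section 3.2 makes Project 4 follow from this pilot's results.

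**Working it through.** **Inputs.** Ratio 1:1 and block length 4 (section 3.5.1); 20 per arm (section 3.5). The documents give no figure for predictability.

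**The plan's own figure.** 40 / 4 = 10 complete blocks, and 10 x 2 = 20 per arm. This reproduces section 3.5.

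**Certain assignments with fixed blocks of 4.** Assume the recruiter knows all earlier assignments in order. The six equally likely blocks are CCBB, CBCB, CBBC, BCCB, BCBC and BBCC (C = CM, B = BSM). The numbers of forced positions are 2, 1, 1, 1, 1 and 2.

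- Mean: 8 / 6 = 4/3 per block, and (4/3) / 4 = 33%. Over 10 blocks: 13.3 of 40.
- The total is 10 + Binomial(10, 1/3). The minimum is 10 (25%), the maximum 20 (50%), and the SD is sqrt(10 x 1/3 x 2/3) = 1.5. The probability of at least 12 is 0.90.

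**Best guessing with fixed blocks of 4.** Guess the arm with more places left. The chances of being right at positions 1 to 4 are 1/2, 2/3, 2/3 and 1. The sum is 17/6, and (17/6) / 4 = 70.8%, or 28.3 of 40 against 20 by chance.

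**Blocks of 4 and 6 in random order.** Simulation of 4,000 lists of 40, with an observer who knows the two possible sizes and all past assignments: 5.6% certain (0.056 x 40 = 2.2 assignments) and 69.0% guessed correctly.

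**Possible bias.** Suppose a recruiter brings in patients whose adherence probability is h above average when CM is expected and h below when BSM is expected. The value of h is assumed; the gap between the two kinds of patient is 2h. If guesses are right with probability g, each arm's mean moves by h(2g - 1), in opposite directions, so the arm difference moves by 2h(2g - 1). If the recruiter acts only on certain assignments, a share s, the shift is 2hs.

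| Situation | Shift in arm difference | h = 5 points | h = 10 points |
|---|---|---|---|
| Fixed 4, acts on every guess (g = 0.708) | 0.83h | 4.2 | 8.3 |
| Random 4/6, acts on every guess (g = 0.69) | 0.76h | 3.8 | 7.6 |
| Fixed 4, acts on certain assignments only (s = 1/3) | 0.67h | 3.3 | 6.7 |
| Random 4/6, acts on certain assignments only (s = 0.056) | 0.11h | 0.6 | 1.1 |
| List visible, acts on every assignment (g = 1) | 2h | 10 | 20 |

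These rows are scenarios, not estimates. They show that varying the blocks nearly removes bias from certain knowledge, does little against guessing, and does nothing if the list can be read.

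**Final balance with 4/6 blocks.** All blocks are even, so at 40 the unfinished part of a block has 2 or 4 places. In either case the arms differ by at most 2, which gives 21/19 at worst. This assumes that the new list starts when a block of 4 has just been completed.

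**The case against.** Several points on the other side have force.

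*Full knowledge is inferred.* A reader might infer that the interventionists do know a third of assignments in advance. The documents do not say so. Section 8.2.3 assigns each participant to one counselor, so each interventionist treats only some participants, and someone who saw only those would be certain of fewer. Shared recordings labelled by condition make fuller knowledge plausible, but it remains an assumption, and 33% and 70.8% depend on it.

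*Visibility of the list is not established.* A reader might infer from section 8.2.3 that recruiters can read it. The section is silent on viewing. The gap is real; the access is not shown.

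*Discretion is limited.* Section 3.5.2 allows unusual treatment schedules "on a case by case basis, dependent upon the ability to complete study procedures within the study timeline", and a reader might take this as wide freedom over entry. It concerns about 5% of new patients (0.05 x 40 = 2), and section 7 asks for physician confirmation of a regular schedule. In the standard pathway the physician identifies and introduces patients. Schedule review by staff and the timing of baseline are the better evidence.

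*This is a pilot.* The SAP puts little weight on significance testing. At 20 per arm, with adherence assumed between 50% and 80%, the 95% half-width for the difference is 1.96 x sqrt(2p(1 - p)/20), or 31 to 25 points, larger than most of the shifts tabulated. That limits the practical weight of the point. It does not remove it: a confidence interval shows random error and not selection bias, and the effect size is what the pilot is meant to deliver.

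*Adjustment is possible in part.* Treatment history, craving and diagnostic severity are collected at baseline (section 12.1), so it would be too strong to say that no analysis could help. Selection on unrecorded motivation would remain.

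**Conclusion.** The concern holds as a weakness in allocation concealment with two parts: a fixed block length known to recruiting staff, and a posted list whose viewing is not restricted. The second could be the larger exposure.

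For a recruiter who knows all earlier assignments in order, at least 25% and on average 33% of assignments are certain, and 70.8% can be guessed. For one who can read the list, all are known. The resulting bias depends on an assumed h and on willingness to act on the knowledge.

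Two stronger conclusions are not supported. Nothing in the documents shows that anyone used such knowledge, so it cannot be said that the comparison is biased, only that it is not protected. Nor would varying the block sizes alone be enough: most of the guessing advantage survives (70.8% to about 69%), so concealing the list is the main correction and some predictability remains after both steps.

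**What to change.** 1. Restrict viewing as well as editing of the list to one person who does not recruit or consent, for example the study statistician mentioned in section 9.2. That person releases each assignment only once consent and baseline are recorded as complete. Say so in section 8.2.3.
2. For remaining enrolment, generate the list with randomly varying block sizes (for example 4 and 6), starting when a block of 4 is complete. Remove the block length from section 3.5.1 and keep it in a file that only the statistician holds. Staff who have read the present text know the old length, which is a further reason to change the list itself.
3. Reconcile section 14 with section 8.2.3. Read literally, section 14 gives a BSM-only handout to participants who take the baseline packet home unfinished, which presupposes that the arm is known before randomization is allowed.
4. If enrolment is complete, report the fixed block length and who could see the list and earlier assignments as a limitation of the CM-BSM comparison.

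The cost is a new list, a short release step for each participant, a few edited sentences, and a final split of at worst 21/19 at 40 participants.

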6. RECRUITMENT PLAN

Recruitment will occur through the CAS clinic and the American Recovery Clinic (ARC). [name] and the other physicians at the clinic will be informed of the eligibility criteria so they can note potential participants. At each patient's visit, the physician will tell the new patient they may be eligible to participate in research that will assist them in adhering to buprenorphine treatment. The physician will make sure to explain that this is not required and is different from what they are receiving as standard treatment. If the patient expresses interest, the doctor will bring the patient to a research room where a research staff member will explain the study. The staff member will check for eligibility, and if eligible, consent the participant. Additionally, staff members may approach the physician or clinic staff in regard to determining some eligibility criteria for the patients after reviewing the clinic's schedule of appointments.

Please see the "Alternative Procedures: COVID" section if in-person recruitment is not possible.

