7. ELIGIBILITY CRITERIA

Participants must meet the following eligibility criteria to participate in this study:

- Present for an appointment at CAS or ARC for buprenorphine-naloxone treatment of OUD
- Be eligible for buprenorphine-naloxone treatment (e.g., Suboxone, Bunavail, Zubsolv) as determined by [name]
- At least 18 years of age or older
- Access to a telephone
- Ability to understand consent procedures
- Physician confirmation of a "regular" initiation visit schedule (to ensure completion within pilot study window)

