12.2.3. Screening Questionnaire

	Inclusion	
1.	Presenting for their intake visit to the Center for Addiction Science for treatment of opioid use disorder	Yes / No If no: Exclude

2.	Access to a telephone	Yes / No If no: Exclude
3.	Eligible for receipt of buprenorphine-naloxone medication (e.g., Suboxone, Bunavail, Zubsolv)	Yes / No If no: Exclude
4.	Able to understand consent procedures	Yes / No If no: Exclude
Exclusion		
5.	Have a known contraindication to buprenorphine-naloxone medication treatment for opioid use disorder	Yes / No If yes: Exclude

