Statistical Analysis Plan: SMART Project 3 (Efficacy Study)

Because these analyses will focus on determining and intervention feasibility and satisfaction, and preliminary intervention effect sizes (with less concern focused on testing for statistical significance), outcome analyses will be conducted using a separate analysis for each outcome at each follow up observation. To compare groups, baseline and follow up variables will be entered into a 5 (baseline vs. follow ups at 1, 2, 3, and 4 weeks) by 2 (CM vs. BSM) analysis of variance (ANOVA) which will yield effect sizes for time, and interactions of time by intervention. The primary dependent variables will be attendance at physician visits, saliva drug screen data (positive for buprenorphine and negative for illicit opioids), and prescription drug monitoring. We hypothesize that a greater number of CM participants will demonstrate adherence to buprenorphine-naloxone than BSM, but that those randomized to BSM will report increased time allocated to substance-free activities, decreased delayed reward discounting, and demand for opioid.

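### The protocol contradicts itself on whether the second clinic (ARC) enrols and how its outcome is captured; if ARC does enrol, clinic appears in neither the allocation nor the analysis

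*Protocol*

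**What the plan says.** **Which clinics.** Protocol section 6 states: "Recruitment will occur through the CAS clinic and the American Recovery Clinic (ARC"). Section 8.1 repeats both clinics, and section 7 lists as an eligibility criterion: "Present for an appointment at CAS or ARC for buprenorphine-naloxone treatment of OUD". Section 3.5 says otherwise: "Approximately 40 participants will be recruited from UTHSC's Center for Addiction Science (CAS) for this study". Section 3.5.2 speaks of eligibility to receive medication at CAS. The screening form (12.2.3) excludes anyone who does not meet "Presenting for their intake visit to the Center for Addiction Science for treatment of opioid use disorder".

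**How the outcome is captured.** Section 3.2 defines efficacy as attending the physician at the Center for Addiction Science plus buprenorphine in urine. The four adherence forms (12.2.7 to 12.2.10, one of them numbered 11.2.9) ask only about a CAS appointment. The urine toxicology form (11.2.12) refers to urine collected by CAS.

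**Allocation.** Section 3.5.1: "Participants are individually assigned to a study arm by block randomization (1:1 allocation, block length of 4"). Section 8.2.3 uses the singular: "The randomization scheme is posted on the" study's OneDrive file. Section 3.5 sets the numbers: "We will randomize 20 participants to the CM group, and 20 participants to the BSM group". No stratification factor is named.

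**Analysis.** The SAP specifies five time points "by 2 (CM vs. BSM) analysis of variance (ANOVA"). It names no clinic term and no other covariate. Neither Table 1 nor section 12.2 lists the recruiting clinic; the referral item (12.2.2) asks only how the person was referred to CAS.

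**The concern.** Adherence combines attendance at routinely booked visits with a urine result from clinical care, so it could plausibly differ between two clinics. Blocks of 4 on a list that ignores clinic balance the arms overall but not within clinic. If the clinics differ in adherence and split unevenly between arms, part of the observed CM-BSM difference reflects clinic rather than intervention. The pilot's product is a preliminary effect size that precedes Project 4, so one realised number is carried forward. Clinic is known for every participant at enrolment, and using it costs little.

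A prior question is how an ARC participant is scored. The attendance item names only CAS. Taken at its word, it would mark an ARC participant non-adherent at every visit, whatever that person did.

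**Working it through.** **1. The plan's own figure.** 40 / 4 = 10 blocks with 2 per arm in each, so 20 per arm. This agrees with section 3.5. The documents give no alpha, power, adherence rate or expected ARC number, so 40 cannot be checked against a power formula.

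**2. Assumptions (not in the documents).** Overall adherence p = 0.50. ARC share q = 0.25 to 0.50 (10 to 20 of 40), with smaller shares as a check. CAS-ARC adherence gap D = 20 to 40 points.

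**3. Chance imbalance without stratification.** With m ARC participants in mixed arrival order, the number X assigned to CM is hypergeometric (40, m, 20). The between-arm gap in ARC share is (2X − m)/20. Simulated lists in blocks of 4 gave essentially the same spread.

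| ARC n | SD of gap | Arms differ by 4 or more ARC participants | 95th percentile of gap |
|---|---|---|---|
| 4 | 0.096 | 11% | 0.20 |
| 10 | 0.139 | 27% | 0.30 |
| 20 | 0.160 | 34% | 0.30 |

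**4. Shift in the realised effect size** = gap × D. At the 95th percentile:
- D = 20 points: 0.20 × 20 = 4 points (n = 4); 0.30 × 20 = 6 points (n = 10 or 20).
- D = 40 points: 0.20 × 40 = 8 points; 0.30 × 40 = 12 points.

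The standard error of the unadjusted difference is √(2 × 0.5 × 0.5 / 20) = 15.8 points.

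**5. Avoidable variance.** Clinic accounts for q(1 − q)D² of the outcome variance p(1 − p) = 0.25. The ratio of unadjusted variance to variance with stratified lists plus a clinic term is 0.25 / (0.25 − q(1 − q)D²), before the small cost of one degree of freedom.

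| Share q | D = 20 points | D = 30 points | D = 40 points |
|---|---|---|---|
| 5% | 0.25/0.2481 = 1.01 | 1.02 | 0.25/0.2424 = 1.03 |
| 25% | 0.25/0.2425 = 1.03 | 1.07 | 0.25/0.22 = 1.14 |
| 50% | 0.25/0.24 = 1.04 | 1.10 | 0.25/0.21 = 1.19 |

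For shares of 25% to 50% the excess is 3% to 19%, equivalent to about 40 × 0.031 = 1 to 40 × 0.19 = 8 participants. This is for a simple two-arm comparison of adherence, used as a proxy for the SAP's time-by-arm model.

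**6. Bias and type I error.** These were simulated with no treatment effect, p = 0.60, and either 10 ARC participants with D = 20 points or 20 with D = 20 or 40 points. The mean unadjusted difference was within 0.2 points of zero. Type I error was 4.7% to 4.9%, the same as with no clinic effect.

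**7. The CAS-only item taken literally.** Suppose CAS adherence is 0.60 and 10 ARC participants all score 0. Then D = 60 points and the 95th percentile shift is 0.30 × 60 = 18 points. Overall adherence is 0.75 × 0.60 = 0.45, so the standard error is √(2 × 0.45 × 0.55 / 20) = 15.7 points. This gap would be an artefact of the form, and correcting the item is the remedy for it.

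**The case against.** The strongest reply is that this is a 40-person pilot concerned with feasibility, satisfaction and preliminary effect sizes, for which an unstratified, unadjusted comparison is legitimate. That stands. At a 20-point gap the gain is 3% to 4% of variance, and the 4 to 6 point shift is well inside a standard error near 16 points.

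No passage says that CAS and ARC differ in booking, visit spacing or testing. Section 7 requires physician confirmation of a regular visit schedule and has one named person determine medication eligibility, which points towards similarity, although section 3.5.2 allows case-by-case exceptions. This also stands: the gap and the ARC share are assumptions. If ARC patients filled consecutive places on the list, the existing blocks would already nearly balance them.

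A reader might draw four stronger conclusions that the documents do not support:
- **That clinic imbalance biases the comparison.** Over repeated randomizations it does not, type I error is unaffected, and the extra variance is already in the unadjusted standard error.
- **That a single unstratified list is confirmed.** This is inferred from the singular wording in section 8.2.3 and from silence on strata.
- **That clinic could never be added later.** Outcomes come from medical charts, so clinic is probably recoverable there, and section 12.2 is not shown to be the full database schema.
- **That ARC participants will be scored non-adherent.** The form reads that way, but nothing says how staff apply it to them.

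The CAS-only passages do not dispose of the point. Sections 6, 7 and 8.1 are the operative recruitment text and include ARC, so the two sets must be reconciled.

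**Conclusion.** The point holds in a limited form. The certain defect is an unreconciled contradiction: three sections recruit at ARC, while the efficacy definition, the sample-size section, the screening form and the attendance and urine items refer to CAS only. If ARC enrols, clinic is a known baseline factor that is absent from the stated allocation, the SAP model and the listed measures.

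The consequence is loss of precision and a possible shift in one realised effect size, not systematic bias. With an assumed ARC share of 25% to 50% and a gap of 20 to 40 points, the unadjusted variance is about 3% to 19% too high. The 95th percentile shift is 6 to 12 points. At a 5% share the variance excess is 1% to 3%, and if ARC enrols no one the allocation and analysis question disappears. The matter would become large only if the clinics differ by about 40 points or more, or if the CAS-only item were applied literally to ARC participants.

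**What to change.** 1. Reconcile sections 3.2, 3.5, 3.5.2, 12.2.3 and the outcome forms with sections 6, 7 and 8.1, stating whether ARC participants are enrolled.
2. If they are, reword the attendance and urine items so that they apply to the participant's own clinic.
3. Add a recruiting-clinic field (CAS/ARC) at enrolment, completed from charts for those already enrolled.
4. Keep a separate list in blocks of 4 for each clinic for participants still to be randomized.
5. In the SAP, estimate the CM-BSM adherence difference with clinic as a factor, or as a clinic-stratified risk difference.
6. Report enrolment and adherence by clinic and arm.

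The cost is some text edits, one field, a second list and one degree of freedom. An unfinished block can leave a difference of at most 2 in each clinic, so two lists run from the start could end at 22 against 18. If randomization is already complete, every step except the fourth can still be done.
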